4.1.2. Baseline Definition

Unless otherwise specified, baseline will be the last value/assessment before the first dose of study treatment (Day 1 pre-dose). If there are multiple assessments collected at the same scheduled time, the average of these assessments will be used as the baseline.

Unless otherwise stated, if baseline data is missing no derivation will be performed and baseline will be set to missing.

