7.1.2. QTc Stopping Criteria

The Fridericia QT correction (QTcF) formula will be used in the study.

A participant that meets either bulleted criteria based on the average of triplicate ECG readings will be considered for withdrawal from the study intervention:

- $QTcF > 500$ msec
- Change from baseline: $QTcF > 60$ msec

Baseline QTcF will be based on the pre-dose ECGs collected before the first dose.

If a clinically significant finding is identified after enrolment, the investigator or qualified designee will determine if the participant can continue in the study and if any change in participant management is needed. This review of the ECG printed at the time of collection must be documented. Any new clinically relevant finding should be reported as an AE.

Note: Single safety ECG assessments are performed following enrolment in this study. If a single ECG should meet the criteria above, obtain two further ECGs over a brief period (e.g., 5 to 10 minutes). The averaged QTcF value of the 3 ECGs should be used to determine whether the participant should be withdrawn from the study.

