8.2.3. Electrocardiograms

- 12-lead ECG safety ECGs will be performed in semi-supine position after at least 10 minutes rest.
- All safety ECGs must be obtained using an ECG machine that automatically calculates the heart rate and measures, PR, QRS, QT and QTcF intervals.
- Safety ECGs will be interpreted on-site by the Investigator to ensure participant safety. At time points where triplicate ECGs are required, the ECGs will be obtained at least 2 minutes apart and over a recording period of up to 10 minutes.
- Baseline QTcF will be based on the predose ECGs collected before the first dose.
- Refer to Section 7.1.2 for QTc specific stopping criteria.
- Refer to the SRM for further information.

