4.2.2.2. Laboratory Data, Vital Signs, ECGs

For haematology, clinical chemistry, urinalysis, vital signs, ECG and spirometry data the following information will be summarised:

- 1) Clinically significant values at each visit
- 2) Raw and change from baseline values at each visit

Note: The first table is the only one included as part of the primary endpoint. Urinalysis data is only collected when there is an abnormal finding and so it is expected that urinalysis tables/listings will be sparse.

Laboratory Data

For laboratory data, separate tables for haematology, clinical chemistry and urinalysis tests will be produced. Laboratory evaluations including the analyses of Clinical chemistry tests, haematology tests and urinalysis, will be based on GSK Core Data Standards. Liver biochemical parameters will be included with clinical chemistry tests.

The details of the planned displays will be given in the OPS. Incidence of clinically significant laboratory parameters will be reported.

Vital Signs

The analyses of vital signs will be based on GSK Core Data Standards, unless otherwise specified.

In vital sign assessment, pulse rate, respiratory rate, tympanic temperature, and systolic and diastolic blood pressure will be assessed. Blood pressure and pulse measurement will be taken in the semi supine position.

Incidence of clinically significant vital sign parameters will be reported. Refer the normal ranges of laboratory parameters in the Section [6.2.1](#)

Further details of the planned displays will be given in OPS.

ECG

The QTc data analysis will use the collected values based on Fridericia formula.

The analysis of 12-lead ECG along with any ECG findings will be reported according to GSK Core Data Standards.

Safety ECGs will be performed in semi-supine position after at least 5 minutes rest. The parameters collected are PR, QRS, QT and QTc intervals.

Incidence of clinically significant ECG parameters will be reported. Refer the normal ranges of laboratory parameters in the Section [6.2.1](#)

Further details of the planned displays will be given in OPS.

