4.2.2.3. Lung Function Measurements

Spirometry

Spirometry data will include FEV1 measurements.

For spirometry data the following information will be summarised:

- 1) Clinically significant values at each visit
- 2) Raw and change from baseline values at each visit

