6.2. Appendix 2 Data Derivations Rule

6.2.1. Criteria for Potential Clinical Importance

- **Laboratory Values**

Haematology				
Laboratory Parameter	Units	Category	Clinical Concern Range	
			Low Flag (<x)	High Flag (>x)
Platelet Count	10 ⁹ /L		31	900
RBC Count	10 ¹² /L		4.2	5.9
Hemoglobin	g/L	Male	90	180
		Female	90	180
Hematocrit	fraction of 1			1.5*ULN
RBC Indices				
MCV	fL		0.75*LLN	1.5*ULN
MCH	pg		28	32
%Reticulocytes	%		na	2*ULN
WBC Count with differentials				
Lymphocytes	10 ⁹ /L		0.6	6
Neutrophil Count	10 ⁹ /L		1.5	12
Monocytes	10 ⁹ /L		na	2
Eosinophils	10 ⁹ /L		na	0.5
Basophils	10 ⁹ /L		na	2*ULN

CONFIDENTIAL

Clinical Chemistry				
Laboratory Parameter	Units	Category	Clinical Concern Range	
			Low Flag (<x)	High Flag (>x)
Albumin	g/L		32	50
Calcium	mmol/L		2.2	3.24
Creatinine	umol/L	Male 40-49 years	69	106
		Male 50-59 years	67.2	106
		Male 60-69 years	67.2	106
		Male 70+ years	59.2	106
		Female 40-49 years	52.2	106
		Female 50-59 years	53	106
		Female 60-69 years	53	106
		Female 70+ years	55.7	106
Glucose	mmol/L		4.0	7.8
BUN	mmol/L		2.5	15
Potassium	mmol/L		3.5	5.2
Sodium	mmol/L		136	145

CONFIDENTIAL

Liver Function			
Test Analyte	Units	Category	Clinical Concern Range
Alanine Aminotransferase (ALT) / Serum Glutamic-Pyruvic Transaminase (SGPT)	U/L	High	≥2x ULN
Aspartate Aminotransferase (AST) / Serum Glutamic-Oxaloacetic Transaminase (SGOT)	U/L	High	≥2x ULN
Alkaline phosphatase	U/L	High	≥2x ULN
T Bilirubin	μmol/L	High	≥ 1.5x ULN
Direct Bilirubin	μmol/L		0 – 6

- **ECG**

ECG Parameters	Unit	Clinical Concern range	
		Lower(<x)	Upper(>x)
Absolute			
Absolute QTc Interval	msec		> 600
Absolute PR Interval	msec	< 85	> 240
Absolute QRS Interval	msec	< 70	> 120
Change from Baseline			
Increase from Baseline QTc	msec		> 60

- **Vital Signs**

Vital Parameters (Absolute)	Unit	Clinical Concern range	
		Lower(<x)	Upper(>x)
Heart rate	bpm	35	110
Respiratory Rate	breaths/pm	8	20
Systolic blood pressure	mmHg	95	160
Diastolic Blood Pressure	mmHg	55	100
Temperature	°C	35.6	37.7

- **Spirometry**

Any participant experiencing a reduction in FEV1 at the 1-hour post-dose compared to daily pre-dose value of > 20%.

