6.2.2. Study Period

Assessments and events will be classified according to the time of occurrence relative to the study intervention period.

Pre-Intervention is defined as time prior to the first dose of study intervention.

On-Intervention is defined as time from first dose to last dose date plus 14 days. If time of assessment or study intervention is not collected, the following assessment on the first dose date will be assumed to be taken prior to the first dose and therefore considered pre-intervention: ECG, Lab, and vital signs, and first dose date is considered on-intervention for AE and concomitant medication.

Post-Intervention is defined as any time post on-intervention window, i.e., > last dose date + 14 days.

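### With one baseline before Period 1, the descriptive change tables for Periods 2 and 3 include any shift since then; a period baseline should be added beside it

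*SAP*

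**What the plan says.** SAP 4.1.2, in the same words as protocol 9.4.1, sets the default: "baseline will be the last value/assessment before the first dose of study treatment (Day 1 pre-dose"). Protocol 8.2.3 adds "Baseline QTcF will be based on the predose ECGs collected before the first dose", and protocol 7.1.2 repeats this for the stopping rule. No section defines a baseline for each period.

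SAP 4.2.2.2 and 4.2.2.3 then ask for "Raw and change from baseline values at each visit" for haematology, chemistry, urinalysis, vital signs, ECG and spirometry. SAP 4.2.2.2 places these change tables outside the primary endpoint. Of the table of clinically significant values it says: "The first table is the only one included as part of the primary endpoint".

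Two criteria in SAP 6.2.1 compare a value with an earlier one. The ECG criterion "Increase from Baseline QTc" (above 60 msec) uses baseline. The spirometry criterion does not: "Any participant experiencing a reduction in FEV1 at the 1-hour post-dose compared to daily pre-dose value of > 20" per cent.

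**The concern.** Protocol Table 1 takes the same 12 participants through three randomised periods, and protocol 4.1 justifies the crossover by its control of differences between individuals. The Schedule of Activities collects pre-dose FEV1, ECG and vital signs on Day 1 of every period, and laboratory tests on Day -1 of every period. Under the stated definition, none of the Period 2 or 3 pre-dose values serves as a reference for change.

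A shift that arose before Period 2 or 3 dosing is therefore counted in the change reported for the later dose, or for placebo. Maintenance COPD medicines are permitted (protocol 6.8) and rescue medication is allowed at any time (protocol 6.8.1), so some movement between periods is plausible. The study tests no hypothesis, so readers will take what each dose does to these measurements largely from the descriptive tables.

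**Working it through.** The plan gives no figure that depends on the choice of baseline, so there is none to reproduce. The check has five steps.

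**1. Which Day 1 is meant.** Every period has a Day 1, and SAP 4.1.2 does not name one. The literal reading is Period 1, because that is when study treatment is first given. Two other places fit this reading. SAP 4.3.1.3 names Period 3 explicitly when it means that period's first dose. SAP 6.2.2 uses a study-wide start: "Pre-Intervention is defined as time prior to the first dose of study intervention". That section classifies events and does not define baseline, so it supports the reading without settling it.

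**2. Elapsed time.** Inputs: single-dose periods of 6 days each (protocol Table 2); at least 5 days between single doses and at least 6 days before Period 3 (protocol 4.1). Period 3 Day 14 is 13 days after Period 3 Day 1.

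| Assessment | From study baseline, 6 + 6 days | From study baseline, 5 + 6 days | From that period's Day 1 |
|---|---|---|---|
| Period 2, Days 1 to 2 | 6 to 7 | 5 to 6 | 0 to 1 |
| Period 3, Day 1 | 12 | 11 | 0 |
| Period 3, Day 7 | 12 + 6 = 18 | 11 + 6 = 17 | 6 |
| Period 3, Day 14 | 12 + 13 = 25 | 11 + 13 = 24 | 13 |

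The rationale text in protocol 4.1 gives 5 days as the minimum before repeat dosing as well, which would make the last row 5 + 5 + 13 = 23. The two statements need reconciling, but the point does not turn on the difference.

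**3. Earlier active exposure.** The sequences are A-P-A, A-A-P, A-A-A and P-A-A, with 3 participants each.

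| Period and arm | n | With earlier active drug | Mean number of earlier active periods |
|---|---|---|---|
| 2, active | 9 | 6 | (1 + 1 + 0)/3 = 0.67 |
| 2, placebo | 3 | 3 | 1.00 |
| 3, active | 9 | 9 | (1 + 2 + 1)/3 = 1.33 |
| 3, placebo | 3 | 3 | 2.00 |

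The 3 placebo participants in Period 3 (A-A-P) have had both 500 and 1000 mcg, so their placebo change starts before two active doses.

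**4. What drift would do.** Each active dose occurs in one period only. Suppose, as an assumption, a common drift of *g* per period step and no drug effect. Within-arm change is then 0, *g* and 2*g* in Periods 1, 2 and 3, which looks like a dose trend. Placebo pooled over periods averages (0 + *g* + 2*g*)/3 = *g*, so the active-minus-pooled-placebo differences are -*g*, 0 and +*g*. Against placebo from the same period the expected difference is 0, but each period has only 3 placebo participants. The SAP does not say which placebo display will be used.

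**5. Whether the size can be derived.** It cannot.
- *Precision.* Let visit-to-visit variation be independent with variance σ², and let a persistent shift between Period 1 and Period 3 have variance τ². Change from the study baseline has variance 2σ² + τ²; change from the Period 3 baseline has variance 2σ². If τ² = 0 the gain is nil. The documents give neither quantity.
- *Carry-over.* The half-life is not stated. The fraction of plasma drug left after 120 to 144 hours is 0.5^(hours/half-life). For assumed half-lives of 12, 24 and 48 hours this is about 0.1% or less, 3.1% to 1.6%, and 17.7% to 12.5%.

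**The case against.** The strongest reply is that a single drug-free baseline is a legitimate choice for safety. By Period 3 everyone has had active drug, so a period baseline would subtract any effect that persists from earlier doses. This stands, and it is why the study baseline should be kept.

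The sources of drift are also partly controlled. Unstable COPD is excluded (protocol 5.2), an exacerbation leads to withdrawal (protocol 7.1.4), and the washout rests on observed PK (protocol 4.1). Raw values are summarised at each visit, so a pre-dose shift in a group could be seen. Display details are left to the output specification, which is not available here. These points limit the likely size of the problem. They do not give the change tables a reference tied to the dose being summarised.

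Three stronger readings are tempting, and the documents do not support them.

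- *That the primary endpoint is compromised.* The change tables are outside it. The FEV1 flag uses the daily pre-dose value and is already protected from drift between periods. The other flags are absolute or limit-of-normal thresholds, apart from the QTc increase.
- *That a stated bias or loss of precision follows.* No between-arm contrast is planned, and step 5 shows that the gain depends on quantities the documents do not contain.
- *That the QTc-increase flag should move to a period baseline.* Protocol 7.1.2 says "Baseline QTcF will be based on the pre-dose ECGs collected before the first dose", which the current flag matches. Take a hypothetical participant who is 40 msec above study baseline before Period 3 dosing and 65 msec above it on Day 14. The study baseline gives 65 > 60 and a flag. The period baseline gives 65 - 40 = 25 and no flag, although the stopping threshold is met.

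**Conclusion.** The point holds for the descriptive change-from-baseline tables in Periods 2 and 3. As written, those tables combine the current treatment with anything that changed since Period 1, over about 24 to 25 days by Period 3 Day 14 where 13 would suffice. Dose is fully confounded with period, and the comparison group is 3 participants who have already had two active doses. That the changes are mixed follows from the definition and Table 1 alone. How much they are mixed is unknown.

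The conclusion rests on the literal reading of the first dose of study treatment. If the sponsor meant each period's first dose, the text still needs correcting because it does not say so. The primary endpoint is touched only through the QTc-increase flag, and there the study baseline should stay. This is a worthwhile and inexpensive improvement to the descriptive safety displays; it does not undermine the study's safety assessment.

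**What to change.** In SAP 4.1.2 and protocol 9.4.1:

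- State that the existing baseline is Period 1 Day 1 pre-dose, and call it the study baseline.
- Add a period baseline: the last value before that period's first dose (Day 1 pre-dose for FEV1, ECG and vital signs; Day -1 for laboratory tests).

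In SAP 4.2.2.2 and 4.2.2.3:

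- Present change from the period baseline for the by-dose summaries, alongside change from the study baseline for cumulative effects.
- State whether placebo is shown by period or pooled.

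In SAP 6.2.1, keep the QTc-increase flag on the study baseline, in line with protocol 7.1.2 and 8.2.3. A period-baseline version may be added as an additional display only. The participant-level stopping rule is not affected.

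The cost is one more derived baseline variable and a second set of change tables. The Schedule of Activities already collects every value needed. Drift within the 14 days of Period 3 would remain under either baseline.

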4.2. Primary Endpoint(s) Analyses

All safety analyses will be performed on the Safety Analysis set, unless otherwise specified.

Primary Endpoints:

- Adverse events (AEs) and serious adverse events (SAEs).
- Clinically significant changes in laboratory values, vital signs, 12-lead ECG, and spirometry measurements up to Follow Up.

4.2.1. Definition of endpoints

Adverse events will be coded using the latest standard Medical Dictionary for Regulatory Affairs (MedDRA dictionary).

Grade 1 AEs are defined as mild. Grade 2 or higher AEs are defined as moderate or severe. This study will report AEs as mild, moderate, or severe.

CONFIDENTIAL

A study intervention-related AE/SAE is defined as an AE/SAE for which the investigator classifies the possible relationship to study intervention as “Yes”. A worst-case scenario approach will be taken to handle missing relatedness data, i.e., the summary table will include events with the relationship to study intervention as ‘Yes’ or missing.

Spirometry assessments are performed in triplicate with the highest value reported.

Whilst all data collected will be summarized, only measurements which are clinically significant at any timepoint between randomization and follow up will be reported as part of the primary endpoint.

Clinically significant values are defined as:

- Values in the potential clinical interest (PCI) ranges for laboratory values, vital signs, ECGs and spirometry.
- Values that achieve the study stopping criteria (protocol Section 7.1.3) for spirometry

The PCI ranges will be defined in the Section [6.2.1](#).

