9.2. Sample Size Considerations

No formal statistical techniques were used to calculate the sample size for this study.

The number of participants included is deemed an adequate number to provide an assessment of safety and tolerability and pharmacokinetics measurements.

Sufficient participants with COPD will be screened and randomized to receive GSK3923868 inhalation powder or placebo in a 3:1 ratio with the intention of a minimum of 8 and a maximum of 12 participants to complete the study.

In total, up to 9 participants are planned to receive each dose of active drug in each period. If the true adverse outcome rate is 5%, the chance of observing at least one adverse event at a given dose is 37%. If the true adverse outcome rate is 20%, the chance of observing at least one adverse event at a given dose level is 87%. For sample size of 6 participants on active drug in each period, if the true adverse outcome rate is 5%, the chance of observing at least one adverse event at a given dose is 27%. If the true adverse outcome rate is 20%, the chance of observing at least one adverse event at a given dose level is 74%.

This level of predictivity is deemed adequate within this phase of development.

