10.2. Appendix 2: Clinical Laboratory Tests

The tests detailed in [Table 4](#) will be performed by the local laboratory.

Protocol-specific requirements for inclusion or exclusion of participants are detailed in [Section 5](#) of the protocol.

Additional tests may be performed at any time during the study as determined necessary by the investigator or required by local regulations.

Table 4 Protocol-required Safety Laboratory Tests

Laboratory Assessments	Parameters			
Hematology	Platelet count	RBC Indices: MCV MCH %Reticulocytes	WBC count with differential: Neutrophils Lymphocytes Monocytes Eosinophils Basophils	
	RBC count			
	Hemoglobin			
	Hematocrit			
Clinical Chemistry ¹	BUN	Potassium	AST)/SGOT	Total and direct bilirubin
	Creatinine	Sodium	ALT)/SGPT	Total protein
	Glucose (non-fasting)	Calcium (corrected)	Alkaline phosphatase ²	Albumin
Routine Urinalysis	
 Specific gravity pH, glucose, protein, blood, ketones, bilirubin, urobilinogen, nitrite, leukocytes by dipstick Upon a positive urine test from leucocytes, blood, nitrite or protein, the Investigator may require further urine analysis such as flow cytometry. Results of the additional analyses will be kept in the database. If the flow cytometry examination shows a different result than the urine sticks, the urine will be investigated by fully automated digital imaging where leukocytes, erythrocytes, and casts in the urine will be analyzed. 			
Pregnancy testing	
 Highly sensitive urine human chorionic gonadotropin (hCG) pregnancy test for women of childbearing potential³ 			
Other Screening Tests	
 Follicle-stimulating hormone and estradiol (as needed in women of nonchildbearing potential only) Alcohol urine test Urine drug screen (to include at minimum: amphetamines, barbiturates, cocaine, opiates, cannabinoids and benzodiazepines; may require urine creatinine analyses) 			

Laboratory Assessments	Parameters
	
 • Serology (HIV antibody, HBsAg, anti- hepatitis B core antibodies (IgM) and hepatitis C virus antibody) • COVID-19 testing will be in line with site procedure

NOTES :

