10.3.2. Definition of SAE

An SAE is defined as any untoward medical occurrence that, at any dose, meets one or more of the criteria listed:

a. Results in death

b. Is life threatening

The term 'life-threatening' in the definition of 'serious' refers to an event in which the participant was at risk of death at the time of the event. It does not refer to an event, which hypothetically might have caused death, if it were more severe.

c. Requires inpatient hospitalization or prolongation of existing hospitalization

- In general, hospitalization signifies that the participant has been admitted (usually involving at least an overnight stay) at the hospital or emergency ward for observation and/or treatment that would not have been appropriate in the physician's office or outpatient setting. Complications that occur during hospitalization are AE. If a complication prolongs hospitalization or fulfills any other serious criteria, the event is serious. When in doubt as to whether "hospitalization" occurred or was necessary, the AE should be considered serious.

- Hospitalization for elective treatment of a pre-existing condition that did not worsen from baseline is not considered an AE.

d. Results in persistent or significant disability/incapacity

- The term disability means a substantial disruption of a person's ability to conduct normal life functions.
- This definition is not intended to include experiences of relatively minor medical significance such as uncomplicated headache, nausea, vomiting, diarrhea, influenza, and accidental trauma (e.g., sprained ankle) that may interfere with or prevent everyday life functions but do not constitute a substantial disruption.

e. Is a congenital anomaly/birth defect

f. Other situations:

- Possible Hy's Law case: ALT \geq 3xULN AND total bilirubin \geq 2xULN (>35% direct bilirubin) or international normalized ratio (INR) >1.5 must be reported as SAE
- Medical or scientific judgment should be exercised by the investigator in deciding whether SAE reporting is appropriate in other situations such as significant medical events that may jeopardize the participant or may require medical or surgical intervention to prevent one of the other outcomes listed in the above definition. These events should usually be considered serious.

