Table 1 Changes to Protocol Defined Analysis Plan	16

VERSION HISTORY

SAP Version	Approval Date	Protocol Version (Date) on which SAP is Based	Change	Rationale
SAP	06 Dec 2022	08-Jul-22	Not Applicable	Original version
Amendment 01	16 Aug 2023	28-Nov-22	Section 6.2.1 updated	Discrepancy between PCI ranges and units provided in SAP and values collected by lab
			Removed wording which mentioned PEF data would be summarised.	PEF is being collected for monitoring purposes only and is not recorded in the eCRF.

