6.2.5. Multiple measurements at One Analysis Time Point

When triplicate ECG assessments are taken, mean of the measurement will be calculated first and summary statistics will be based on the calculated mean. This will apply to both baseline and post baseline assessments.

For lab tests on a study day, if more than one assessment is taken on the same day, the test from a central lab will be taken over the test from a local lab. If multiple assessments are taken from the same type of lab, the worst case will be used.

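### SAP 6.2.1 gives direct bilirubin a concern range of 0 to 6 µmol/L with no direction; read literally with SAP 4.2.1, low values are flagged and elevations are not

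*SAP*

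**What the plan says.** SAP 4.2.1 defines clinically significant values as "Values in the potential clinical interest (PCI) ranges for laboratory values, vital signs, ECGs and spirometry", and it points to SAP 6.2.1 for the ranges. SAP 4.2.2.2 plans two displays for laboratory data, the clinically significant values and the raw and change-from-baseline values. It adds that "The first table is the only one included as part of the primary endpoint". Liver tests are placed with clinical chemistry.

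In the Liver Function table of SAP 6.2.1, ALT, AST and alkaline phosphatase carry the category High with a limit of at least 2×ULN. Total bilirubin carries High with at least 1.5×ULN. The last row, "Direct Bilirubin", has an empty category and 0 to 6 µmol/L in the concern-range column.

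Protocol Appendix 2, Table 4, requires "Total and direct bilirubin" in every clinical chemistry panel. The SAP version history shows that Amendment 01 revised Section 6.2.1, with the rationale "Discrepancy between PCI ranges and units provided in SAP and values collected by lab". The 0 to 6 entry is therefore current text.

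**The concern.** The rule in SAP 4.2.1 works only if being in the range means being abnormal. That holds for the other liver rows, where the range starts at a multiple of the ULN. It fails for direct bilirubin, where the listed range begins at zero and looks like a reference interval.

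The protocol regards high direct bilirubin as the signal. The liver follow-up notes in Appendix 6 link direct bilirubin elevations to liver injury, and the possible Hy's law definition includes a direct fraction above 35%. A row that captures 0 to 6 and passes over higher values points the other way.

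At stake is one row of the only laboratory display that counts toward the primary endpoint. As written, that row would list unremarkable results as clinically significant and omit elevations.

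**Working it through.** **1. Is the row an exception?** Rows in SAP 6.2.1:
- haematology: 13 (hemoglobin counted by sex)
- clinical chemistry: 14 (creatinine counted as 8 age and sex rows)
- liver function: 5

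Total 13 + 14 + 5 = 32. The 27 haematology and chemistry rows sit under low (<x) and high (>x) columns, and four liver rows carry ≥. So 27 + 4 = 31 rows have a direction and one does not.

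**2. What does the literal rule flag?** Flag if 0 ≤ value ≤ 6, compared with three possible corrections. The last two assume that 6 is the direct-bilirubin ULN, which the documents do not state: 1.5 × 6 = 9 (the multiple used for total bilirubin) and 2 × 6 = 12 (the multiple used for the other three liver rows).

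| Direct bilirubin (µmol/L) | Literal, 0 to 6 | >6 | ≥9 | ≥12 |
|---|---|---|---|---|
| 0, 2, 4, 6 | flagged | no | no | no |
| 6.1, 7 | no | flagged | no | no |
| 10 | no | flagged | flagged | no |
| 20, 50 | no | flagged | flagged | flagged |

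The literal rule and the >6 rule are exact opposites. The corrections also differ among themselves (see 7 and 10), so the repair is not automatic.

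**3. How many results can be affected?** Randomization is on Day 1 of Period 1. Scheduled safety-laboratory samples after that, from the protocol's Schedules of Activities:
- Period 1: 1 (Day 2)
- Period 2: 2 (Day -1 and Day 2)
- Period 3: 3 (Day -1 and two later)

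That is 1 + 2 + 3 = 6 per completer. The protocol intends "a minimum of 8 and a maximum of 12 participants to complete the study", so 12 × 6 = 72 or 8 × 6 = 48 samples. These are ceilings, not expected flags.

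The documents give no distribution for direct bilirubin. If a share of 0.80 to 0.99 of results lies in 0 to 6 (assumption), the literal rule flags 72 × 0.80 = 57.6 to 72 × 0.99 = 71.3 of 72. A >6 rule flags 72 × 0.20 = 14.4 down to 72 × 0.01 = 0.7.

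**4. Does the total bilirubin row close the gap?** It flags at 1.5×ULN or more. With an assumed ULN of 17 to 21 µmol/L (not in the documents), that is 1.5 × 17 = 25.5 to 1.5 × 21 = 31.5. Direct 10 with total 25 is 10/25 = 40% direct, and neither bilirubin row flags it. So the gap is not closed. The documents do not allow an estimate of how often this would occur.

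**5. Is a possible Hy's law case lost?** No. The definition requires ALT of at least 3×ULN, which exceeds the ALT limit of 2×ULN, so the ALT row always flags it. The total bilirubin row also flags a case that qualifies through bilirubin (2×ULN exceeds 1.5×ULN), but it need not flag one that qualifies through INR. Either way the protocol's SAE definition applies, with the condition ">35% direct bilirubin) or international normalized ratio (INR) >1.5 must be reported as SAE".

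**The case against.** The strongest reply is that 0 to 6 is plainly a reference interval and will be programmed as one. Three things support this.
- Where SAP 6.2.1 gives two numbers for a laboratory test, such as sodium 136 and 145 or potassium 3.5 and 5.2, values outside the pair are flagged.
- SAP 4.2.2.2 twice describes the entries of 6.2.1 as normal ranges.
- Laboratory analyses follow the sponsor's core data standards, with display details in the OPS. Neither is available here.

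The empty category cell may also be a loss in the table as read.

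Much of this stands. It makes a misplaced reference interval the likely explanation. A reader might infer that the study report will show inverted flags; the documents do not support that prediction, only that the plan as written specifies them.

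It does not settle the row. The normal-range wording appears only in the vital signs and ECG paragraphs, and applied to the liver table it would make ALT of at least 2×ULN normal. SAP 4.2.1 assigns the ranges to 6.2.1, not to the OPS. Restoring a High label would still leave 0 to 6 as the listed range. No text gives the intended limit.

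A reader might also see a further fault in SAP 6.2.5, which says "If multiple assessments are taken from the same type of lab, the worst case will be used" without a direction. That is no particular defect of this row: the same holds for every two-sided row, such as sodium, potassium and glucose.

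**Conclusion.** The direct bilirubin entry is wrong as written. It has no direction and, combined with the in-range rule, it flags 0 to 6 µmol/L and leaves elevations unflagged. This conclusion needs no assumption beyond reading SAP 4.2.1 and 6.2.1 together. The ULN values, the share of results within 0 to 6 and the 9 and 12 µmol/L limits are assumptions used only to show scale.

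The size is one row of one table, in a study that tests no formal hypothesis. A reader might infer a risk to participants or a missed liver signal. The documents do not support that: liver stopping criteria and SAE reporting do not use this row, the other four liver flags work, and values above 6 remain in the raw and change-from-baseline summaries. It is a minor correction.

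**What to change.** In SAP 6.2.1, mark direct bilirubin as High and replace 0 to 6 with an explicit upper limit, so that being in the range means elevated. Use above 6 µmol/L if the sponsor confirms that 6 is the laboratory's upper limit, or a stated multiple of the ULN. Either form is acceptable, since other chemistry rows already use absolute limits.

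The cost is one table row and one confirmation from the laboratory, with no new data and no new display.
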